Assessment by Ultrasound of the degree
of venous dilatation, comparison
between venodilation by Airglove™
versus Warm Water Immersion (WWI)

HLS/PSAWAHS/18/168

25th March 2019

Title: Assessment by Ultrasound of the degree of venous dilatation, comparison between venodilation by Airglove™ versus Warm Water Immersion (WWI)

Researcher: [name] [contact],

Supervisors: [name], [name] [name]

Background Information:

Failure to cannulate to gain intra-venous access is a common occurrence in patients undergoing chemotherapy, obese patients, intravenous drug users and those with chronic medical problems leading to peripheral venous collapse. Difficulty in gaining IV-access is a serious medical consequence since important life-saving drugs, fluids, blood transfusions, and other medication are usually given via the intravenous route. Most chemotherapy units in the UK rely on venous dilation by immersing the forearm of patients with “difficult to cannulate veins” (DTCV) into a bucket of warm water. There are however, limitations in this method such as controlling water temperature and ensuring proper sterility.

A new device Airglove™ has been developed which directs warm air over the forearm in a polythene sleeve causing venodilation. Preliminary studies in chemotherapy patients suggest that the Airglove™ causes venodilation to the extent of the warm water immersion technique, however further evidence is required with testing on normal healthy volunteers.

Aims and Objectives:

To determine whether Airglove™ warming device dilates upper limb veins to the same degree as the warm water immersion (WWI) method.

Participants and Recruitment Methods:

Students and staff (n=30) from the School of Health and Life Sciences, who fit the inclusion/exclusion criteria, will be invited via email to take part in this non-invasive study. A participant information letter and consent form have been drawn up to ensure appropriate informed consent is obtained. Details of gatekeeper access authorisation and a recruitment email are included with this application.

Inclusion Criteria:

- * Participants > 18 years old
- * Able to give written informed consent
- * Able to understand and complete questionnaire forms independently

Exclusion Criteria:

- * Participants < 18 years old
- * Participants with cancer and/or undergoing chemotherapy
- * Participants with difficult to cannulate veins (DTCV)
- * Participants with lymphoedema in either hand

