- * Participants with pre-existing Raynaud's disease
- * Participants with Diabetes (Type 1 & 2)
- * Participants with generalised anxiety disorder
- * Participants with diagnosis of hypertension
- * Participants with any cardiovascular disease, previous stroke, episodes of DVT, recent treatment for venous thromboembolism (VTE), recently administered heparin, participants on warfarin or any anticoagulant treatment (including NOACs).
- * Participants not able to give written informed consent
- * Participants not able to comprehend or complete questionnaire forms independently

Design and Methods:

A prospective comparative study will take place in one of the ward areas of the Govan Mbeki Building, GCU Glasgow campus. Participants will expect to give up approximately 50 minutes to take part in the study. No payment or incentive will be offered.

Procedure:

- Anonymised participant demographic (age, gender, height, weight, body fat percentage, basal temperature and hydration status) data will be recorded electronically.
- Participants will be placed in a semi-recumbent position, while measurements are taken of the both arms. Blood pressure measurements will also be taken.
- Baseline 2D ultrasound long and short axis measurements of the dorsal metacarpal vein at the wrist and cephalic and median cubital veins of the cubital fossa will be taken.

Airglove™ Method Assessment:

- Select temperature setting at 38.5°C. Gently slide plastic sleeve onto RIGHT arm of volunteer, start machine. Airglove will warm the air for 3 minutes and will automatically stop.
- Discard the plastic sleeve and dispose of this as per GCU practice for recyclable plastics policy. (Sleeve is single use only).
- Carry out ultrasound examination of all 3 veins and record vein dimensions.
- Allow participants to rest 10 minutes before crossing to WWI method.

Warm Water Immersion Method Assessment:

- Collect warm water (from tap) into a bucket. Adjust the temperature of the water to 38.5° using titration of cold water
- Immerse entire RIGHT forearm of the volunteer into the bucket for 3 minutes. Remove arm and pat dry with appropriate towelling.
- Carry out ultrasound examination of all 3 veins and record the vein dimensions.

Repeat Airglove and warm water immersion procedures for participants LEFT arm.

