**Assessment by Ultrasound of the
degree of venous dilatation,
comparison between venodilation
by Airglove™ versus Warm Water
Immersion (WWI)**

HLS/PSAWAHS/18/168

30th April 2019

Statistical analysis and sample size calculations

This study enrolled 34 participants, a minimum sample size of 24 was required for 90% power, $\alpha = 0.05$ and the ideal anticipated Cohen's "d" effect size of 0.833, calculated using the "pwr.T.test" module in R version 3.60 ^{9 10}. Mean venodilation by WWI and AirGloveTM for input into the "pwr.T.test" script was determined from previous pilot studies carried out at the Sir Geraint Evans Wales Heart Research Institute, Cardiff. All statistical analysis was carried out with SPSS ver.25 (IBM Corp), SciPy module (ver 1.3) for Python (ver 3.7.2) and R version 3.60 with $P<0.05$ considered as statistically significant.

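### No scan is planned just before warm water immersion, and Airglove is named first on both arms, so residual dilatation or drift could bias the comparison without being measured directly

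*Protocol*

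**What the plan says.** The protocol's aim (Aims and Objectives) is to find out whether Airglove "dilates upper limb veins to the same degree as the warm water immersion (WWI) method".

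Under Design and Methods, Procedure, participants lie semi-recumbent "while measurements are taken of the both arms". One baseline is listed, before any warming: "Baseline 2D ultrasound long and short axis measurements of the dorsal metacarpal vein at the wrist", plus two veins at the elbow.

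The right arm then goes through these steps in order:

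- Airglove for 3 minutes, then a scan of the three veins.
- The instruction "Allow participants to rest 10 minutes before crossing to WWI method".
- "Collect warm water (from tap) into a bucket", temperature adjustment, and immersion of the same forearm for 3 minutes.
- A second scan of the three veins.

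No scan is listed during or at the end of the rest. For the other side the protocol says only: "Repeat Airglove and warm water immersion procedures for participants LEFT arm". It states no random, alternating or reversed order.

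The SAP (Statistical analysis and sample size calculations) names no test or unit of analysis, and no period, sequence or carry-over term. It does not say which baseline WWI dilatation is measured from. It reports: "This study enrolled 34 participants, a minimum sample size of 24 was required for 90% power". The protocol planned n=30.

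**The concern.** Both methods warm the same arm, and the second starts 10 minutes after the scan that follows the first. Whether the veins have returned to their starting size by then is an obvious question, and the plan collects no direct answer. The post-Airglove scan comes before the rest, so it shows the dilated state and not the recovered one.

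If Airglove comes first on both arms, method and period coincide. Anything that changes between the first and second warming (residual dilatation, or drift from lying still, room temperature or hydration) is then attributed to the method. Adding participants or the second arm does not average it out; it only narrows the interval around a shifted value.

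The aim makes this matter in both directions. A shift could produce a difference between equivalent methods. It could also cancel a real difference, and that result would look like the equality the study is asking about.

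**Working it through.** **Inputs.** From the protocol: 3 minutes' Airglove, 10 minutes' rest, 3 minutes' WWI, about 50 minutes in all, n=30 planned. From the SAP: 34 enrolled, minimum 24, α=0.05. The documents give no estimate of residual dilatation, drift or scan error, so every bias size below is assumed.

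**1. Does the baseline protect the contrast?** Let B be the pre-Airglove baseline, A the post-Airglove size and W the post-WWI size on one arm.

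- Absolute change: (A−B)−(W−B) = A−W.
- Ratio: (A/B)/(W/B) = A/W.
- Percent change: (A−B)/B−(W−B)/B = (A−W)/B, a rescaling only.

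B drops out or merely rescales, so it neither detects nor corrects a changed state before immersion.

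**2. How far is the baseline from WWI?** On the right arm, at least 3+10 = 13 minutes plus one scan set. On the left arm, if both arms are scanned at the start and the rest is repeated, at least 3+10+3+3+10 = 29 minutes plus three scan sets.

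**3. What would a bias in A−W do?** Assume a two-sided paired t-test at 0.05, one value per participant, no true difference, and a net bias b in A−W, in SDs of the paired difference. The rejection rate is P(|T|>t(0.975, n−1)), where T is noncentral t with n−1 degrees of freedom and noncentrality b√n. For n=34 and b=0.2, the noncentrality is 0.2×√34 = 1.166 and the critical value 2.035, giving 0.205.

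| b (SD) | n=24 | n=30 | n=34 |
|---|---|---|---|
| 0.1 | 0.076 | 0.083 | 0.087 |
| 0.2 | 0.156 | 0.185 | 0.205 |
| 0.3 | 0.291 | 0.355 | 0.397 |
| 0.4 | 0.467 | 0.563 | 0.620 |

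These rates refer to a bias in A−W itself. They carry over to a pre-immersion shift of the same size only if that shift adds to the WWI response and persists to the post-WWI scan.

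**4. The SAP's sample size.** With d=0.833 read as a two-sided paired effect, 90% power needs 18 participants (17.2 before rounding), not 24. A one-sided unpaired calculation comes closest, at 26 per group (25.4). Since 24 does not follow from a paired reading, I quote no power loss for the masking direction. This point does not depend on the SAP's figure.

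**5. What varying the order would do.** Let δ be the true Airglove−WWI difference, π the drift from first to second period, and λA, λW the carry-over from each method into the other. Airglove first gives δ−π−λA; WWI first gives δ+π+λW. With equal numbers in each order, the mean is δ+(λW−λA)/2. Drift and equal carry-over cancel; half of any inequality in carry-over remains.

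**6. What a pre-second-method scan B2 would do.** The mean of B2−B has a 95% CI half-width of t(0.975, n−1)/√n in SDs of that change: 2.035/√34 = 0.35 at n=34 and 2.069/√24 = 0.42 at n=24.

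**7. Time.** If the rest is repeated on the left arm, the timed steps take 2×(3+10+3) = 32 minutes, leaving 50−32 = 18. With one baseline set per arm there are six scan sets, so a set can average at most 18/6 = 3.0 minutes, less the time for demographics, blood pressure and water preparation.

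**The case against.** The strongest reply is that the plan has a safeguard: 10 minutes' rest after only 3 minutes' warming. Nothing in the documents shows that this is too short, and it may be ample. That stands, and it rules out any claim that carry-over occurred. But the documents give no evidence for the interval, and no planned scan tests it.

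A reader might infer that any shift at the start of immersion must enter the comparison. It need not. If immersion brings veins to the same end size whatever their start, or the residual fades during the 3 minutes, A−W may be little affected. Carry-over and drift may also offset each other. The supportable word is could.

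A reader might also take the left-arm order as fixed. The protocol names Airglove first there but does not say expressly that the sequence must be kept. The alignment of method with period follows from reading the plan as written, and the order actually used has to be confirmed.

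Nor is drift wholly invisible. If both arms are scanned at the start, left-arm Airglove falls at least 3+10+3 = 16 minutes, plus scans, after right-arm Airglove. A left-right difference in Airglove change then carries some information about drift, though it is confounded with side. It says nothing direct about local carry-over into WWI.

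Finally, the SAP already reports 34 enrolled, so design changes may come too late for everyone. That limits the remedy, not the point.

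**Conclusion.** The concern holds as a gap in design and reporting. As written, the plan does not measure vein size at the start of WWI, states no variation in order, and relies on a baseline that cancels from the contrast of interest. A bias from residual dilatation or drift is possible, and the planned scans would not measure it directly.

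Its size and direction are unknown. Under the assumptions stated (two-sided paired t-test, one value per participant, no true difference, bias in A−W itself), a net bias of 0.2 or 0.4 SD of the paired difference gives false-difference rates of 20% or 62% at n=34 and 16% or 47% at n=24. These show sensitivity; they do not estimate what happened.

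The documents do not support the conclusion that the comparison is invalid or that Airglove's effect spilled into WWI. They support a narrower one: a finding that the methods dilate equally, or unequally, rests on an unverified assumption of adequate washout and negligible drift. The design gap is clear from the text; its practical importance is uncertain. The point deserves action because the remedy is cheap.

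**What to change.** **For anyone still to be measured**

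1. Randomise or alternate which method comes first across participants, or reverse it between arms. Record the order used on each arm and include period in the analysis. This averages out drift and symmetric carry-over, but not unequal carry-over. If the order is reversed between arms, vary which arm gets which order, so that order is not tied to side.
2. Rescan the three veins on each arm at the end of the existing rest, just before the second method. Report that size minus the original baseline, with its 95% CI, as combined carry-over and drift. It includes scan error and cannot separate the two. With half-widths of 0.35 to 0.42 SD, a non-significant result does not prove washout.
3. Report the contrast with each method measured from its own pre-warming scan as a sensitivity analysis only. Do not choose between contrasts on the result of step 2. The rescan alone does not remove order bias from A−W; step 1 is the main change.

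**Cost.** Water must be ready for either order. There are two extra short non-invasive scan sets per participant, with equipment already in use. At about 3 minutes or less each they fit within the rest, though they interrupt it and compete with water preparation. The sensitivity contrast carries some added measurement noise.

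**For participants already measured.** Neither change is possible. Report the order actually used on each arm. State that, where Airglove came first, WWI dilatation is measured from a pre-Airglove baseline and that washout was not verified. Limit the conclusion about equal dilatation accordingly. This costs a few sentences.

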**Assessment by Ultrasound of the
degree of venous dilatation,
comparison between venodilation
by Airglove™ versus Warm Water
Immersion (WWI)**

HLS/PSAWAHS/18/168

30th April 2019

Statistical analysis and sample size calculations

This study enrolled 34 participants, a minimum sample size of 24 was required for 90% power, $\alpha = 0.05$ and the ideal anticipated Cohen's "d" effect size of 0.833, calculated using the "pwr.T.test" module in R version 3.60 ^{9 10}. Mean venodilation by WWI and AirGloveTM for input into the "pwr.T.test" script was determined from previous pilot studies carried out at the Sir Geraint Evans Wales Heart Research Institute, Cardiff. All statistical analysis was carried out with SPSS ver.25 (IBM Corp), SciPy module (ver 1.3) for Python (ver 3.7.2) and R version 3.60 with $P<0.05$ considered as statistically significant.

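### The SAP's minimum of 24 for 90% power does not follow from a d of 0.833 entered into a paired or independent two-sided t-test, and the SAP names neither the test nor the SD

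*SAP*

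**What the plan says.** The SAP's single section on statistical analysis and sample size reports 34 enrolled and says that "a minimum sample size of 24 was required for 90% power". It gives alpha as 0.05 and an "effect size of 0.833, calculated using the" t-test power routine in R. The only pilot input described is "Mean venodilation by WWI and AirGloveTM for input into the" routine. No pilot SD, within-person correlation or dropout allowance is given. The section does not say whether the test is paired or two-sample, one- or two-sided, or whether 24 counts participants, arms or one group.

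The protocol (Participants and Recruitment Methods) plans for "Students and staff (n=30) from the School of Health and Life Sciences" and gives no calculation. Its Procedure makes the comparison within person. After the Airglove step on the right arm the instruction is "Allow participants to rest 10 minutes before crossing to WWI method", and after the water step it is "Repeat Airglove and warm water immersion procedures for participants LEFT arm". There are no independent groups.

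**The concern.** The SAP gives n, power, alpha and d, so a reader should be able to check any one of them from the other three. Here that fails: with d used as stated, neither the paired test that fits the design nor an independent-groups test returns 24.

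This is the only power statement in either document. If 0.833 is the paired effect size, the stated 90% at 24 is too low. If the calculation treated the two methods as independent groups, it is too high and the calculation ignored the design. If 0.833 was standardised by the between-person SD, the answer depends on a correlation that is not reported. A reader cannot tell which case applies, so the 90% cannot be relied on.

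**Working it through.** **Inputs from the SAP:** d = 0.833, alpha = 0.05, power = 90%, n = 24, enrolled 34. **From the protocol:** each participant receives both methods on each arm. **Not stated, so varied below:** sidedness, test type, the SD behind d, and the unit of n. The paired figures assume one difference per participant.

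**Method.** Exact noncentral-t power:
- Paired: noncentrality d × √n, df = n − 1.
- Independent, n per group: noncentrality d × √(n/2), df = 2(n − 1).

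For example, at n = 24 two-sided, the paired noncentrality is 0.833 × √24 = 4.08 on 23 df. The independent one is 0.833 × √12 = 2.89 on 46 df.

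**Step 1: try to reproduce 24 with d entered directly.**

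| Test | n for 90% power | Power at 24 |
|---|---|---|
| Paired, two-sided | 17.18 → 18 | 97.4% |
| Paired, one-sided | 13.81 → 14 | 99.0% |
| Independent, two-sided | 31.28 → 32 per group | 80.6% (24 per group) |
| Independent, one-sided | 25.39 → 26 per group | 88.5% (24 per group) |

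If 24 were the total of two groups of 12, two-sided power would be about 50%. None of these gives 24 at 90%. Rounding in d (0.8325 to 0.8335) moves each n by at most 0.04 and changes no whole number.

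**Step 2: look for any route to 24.**
- *Independent, two-sided, 80% power:* 23.62, so 24 per group. This matches the n but not the stated power or the design.
- *Independent, one-sided, 90% power:* 26 per group, which is close but not 24. The SAP states no one-sided test.
- *18 inflated for 25% dropout:* 18 / 0.75 = 24. No dropout allowance appears in either document.
- *Paired, with 0.833 on the between-person SD:* the paired effect size is then 0.833 / √(2(1 − ρ)), where ρ is the within-person correlation. Two-sided, with assumed values of ρ:

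| Assumed ρ | n for 90% power | Power at 24 | Power at 34 |
|---|---|---|---|
| 0 | 32.27 → 33 | 78.9% | 91.5% |
| 0.3 | 23.21 → 24 | 91.0% | 97.9% |
| 0.5 | 17.18 → 18 | 97.4% | 99.7% |
| 0.7 | 11.18 → 12 | 99.9% | >99.9% |

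Rounding up gives 24 only for ρ between 0.274 and 0.307.

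**Step 3: what the 34 enrolled give at d = 0.833, two-sided.** Paired with d direct, 99.7%; independent with 34 per group, 92.3%; paired with between-person d and zero correlation, 91.5%. With 90% power, a paired two-sided test on 34 participants detects 0.57 SD of the within-person differences (0.69 at n = 24).

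**The case against.** The strongest reply is that 24 is not impossible. The SAP does not say which SD standardises d. If it is the between-person SD, a correlation near 0.3 gives exactly 24 from a paired two-sided test at 90% power, and nothing in the documents rules that out. The pilot work may hold the SD or correlation; that the SAP mentions only means does not show that no SD was used. This stands as a limit on the conclusion: no particular arithmetic slip is proven, and the match to 80% power with independent groups is only a coincidence worth checking. It does not rescue the sentence, because that route needs an input the SAP does not state and works only in a narrow band of correlations.

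The second reply is that little turns on this now. On the direct paired reading 24 is conservative, and 34 were enrolled. That is right, and it is why no shortfall is claimed. Adequate enrolment does not make the stated justification correct or checkable.

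The third is that the unit of n is not stated, so the paired powers rest on an assumption of one difference per participant. That also stands, and it is one of the things the SAP needs to settle.

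**Conclusion.** The concern holds. With d = 0.833 entered directly and alpha 0.05, two-sided, 90% power needs 18 participants (paired) or 32 per group (independent), not 24. At 24 the power is 7.4 percentage points above the stated 90% if paired (97.4 − 90) and 9.4 points below it with 24 per independent group (90 − 80.6). If d is on the between-person SD, power at 24 runs from 78.9% to 99.9% over assumed correlations of 0 to 0.7.

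The conclusion is that the stated inputs do not by themselves produce the stated n; it does not identify the calculation that was run. It rests on exact t-test power and, for the paired figures, on one difference per participant. Enrolment of 34 is sufficient at this d on all the two-sided readings examined with 34 per condition, so this should be corrected but does not threaten the study's size. The choice of vein, averaging over arms and any equivalence margin are separate questions.

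**What to change.** Rerun the calculation as a paired, two-sided t-test to match the within-person design, and restate the SAP sentence so that n, power, alpha and d agree. The restated text should:

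- say that n counts participants;
- state which SD standardises d;
- if 0.833 is the mean difference over the SD of within-person differences, give the minimum as 18 participants;
- if it is on the between-person SD, give the pilot correlation and the n that follows. If the pilot gave no correlation, say so and report the range (33, 24, 18 or 12 at assumed correlations 0, 0.3, 0.5 or 0.7);
- if the calculation was not paired and two-sided, say what was run and correct the power or the n.

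It would also help to report the difference detectable with 90% power at the enrolled 34 (0.57 SD of the within-person differences), since that does not depend on how 0.833 was defined.

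The cost is one calculation and one or two rewritten sentences. It needs the pilot SD of differences or the correlation, or a statement that neither is held. No new data, participants or procedures are needed.
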